#### 4.4 Rationale for study population

Per [Section 1.1](#) above, the epidemiology search has shown that the incidence of patients with GEP-NETs per 100,000 population is 0 for the group aged 0 to <12 years, and 0.21 for those aged 12 to < 17 years. The incidence of PPGLs in pediatric patients is even smaller with only single cases recorded in [SEER registry](#) in 2019, corresponding to a rate lower than 0.03 per 100,000 population ([SEER registry](#)). In view of these epidemiology data, the study population will include adolescent patients 12 to <18 years of age.

Patients will be included in the GEP-NET cohort if there is a presence of metastasized or locally advanced, inoperable (curative intent) histologically proven, well differentiated GEP-NET. This population was chosen in line with the indication approved for the adult population.

For PPGL cohort, patients with metastasized or locally advanced, inoperable (curative intent), histologically proven PPGL will be enrolled. This population was selected based on unmet need and mimics adult population with PPGL that has been treated with Lutathera so far.

As Lutathera binds to SSTR2 to deliver tumoricidal radiation to the tumor tissue, the SSTR expression will be confirmed before the 1st Lutathera dose by an SRI modality.

As this is the first prospective clinical study of Lutathera in the pediatric GEP-NET and PPGL populations, a set of safety eligibility criteria will be implemented in the trial to exclude patients with significant hematological, renal and liver impairment, defined as:

- Estimated creatinine clearance calculated by the Cockcroft-Gault method < 70 mL/min
- Hb concentration <5.0 mmol/L (<8.0 g/dL); WBC <2x10^9/L; platelets <75x10^9/L
- Total bilirubin >3 x ULN for age
- Serum albumin <3.0 g/dL unless prothrombin time is within the normal range

These exclusion criteria were chosen in line with the criteria used in the adult NETTER-1 study, except for the estimated creatinine clearance. In the NETTER-1 study, subjects were excluded if creatinine clearance was below 50 mL/min calculated by the Cockcroft-Gault method. As a precaution and as this is the first study in the pediatric population, a higher creatinine threshold was chosen in order to reduce the risk to reach a cumulative renal absorbed dose above 29 Gy (assumed limit for kidney toxicity).

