Any suspected transmission via a medicinal product of an infectious agent is also considered a serious adverse reaction.

All reports of intentional misuse and abuse of the product are also considered serious adverse event irrespective if a clinical event has occurred.

Treatment-emergent elevations in AST or ALT ( $> 3 \times \text{ULN}$ ) in combination with total bilirubin  $> 2 \times \text{ULN}$  or jaundice in the absence of cholestasis (defined as ALP  $< 2 \times \text{ULN}$ ) or other causes of hyperbilirubinemia can be an indicator of severe drug induced liver injury (Hy's Law). The Hy's Law criteria may be changed to increases of transaminases 2-fold above baseline values for subjects with elevated baseline values. For this reason, a potential Hy's Law case requires expedited reporting, and will be handled as a serious unexpected adverse event

(assessing it as medically significant in the absence of any other seriousness criteria). It must be reported as an SAE to the sponsor promptly (i.e., even before all other possible causes of liver injury have been excluded). Reporting should include all available information, especially that needed for evaluating the diagnosis, severity and likelihood that the study treatment caused the reaction. For patient monitoring and to better understand potential etiologies, the investigator must initiate a close follow-up until complete resolution of the problem and completion of all attempts to obtain supplementary data.

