## Liver function parameters

Liver function parameters of interest are total bilirubin (TBL), Alanine Aminotransferase (ALT), Aspartate Aminotransferase (AST) and alkaline phosphatase (ALP). The number (%) of participants with worst post-baseline values will be summarized:

The following summaries will be produced:

- ALT or AST > 3xULN
- ALT or AST > 5xULN
  - TBL > 2xULN
  - ALT or AST > 3xULN & TBL > 2xULN
  - ALT or AST > 3xULN & TBL > 2xULN & ALP < 2xULN

Of note, combined elevations (i.e. last 2 categories) are based on the peak values at any post-baseline time for a participant and thus do not need to be concurrent.

Liver function parameters will be listed, and periods of assessment (screening, on-treatment, short term and long term follow-up) will be flagged.

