## 2.6.5 Other safety data

### 2.6.5.1 ECG and cardiac imaging data

12-lead ECGs including PR, QRS, QT, QTcF, and RR intervals will be obtained for each participant during the study. ECGs are reviewed locally by each investigative site and assessed centrally.

The summaries will include all on-treatment assessments available no later than 56 days after the last study treatment administration date (see Section 2.1.1).

The following summaries will be presented:

- Change from baseline for ECG parameters by timepoint.
- Number and percentage of patients with on-treatment notable ECG values.
  - QT or QTcF
    - New value of > 450 and ≤ 480 ms
    - New value of > 480 and ≤ 500 ms
    - New value of > 500 ms
    - Increase from baseline of > 30 ms to ≤ 60 ms
    - Increase from baseline of > 60 ms
  - HR (=60/RR in seconds)
    - Increase from baseline >25% and to a new HR > 100 bpm
    - Decrease from baseline >25% and to a new HR < 50 bpm
  - PR
    - Increase from baseline >25% and to a new PR > 200 ms
    - New PR > 200 ms
  - QRS
    - Increase from baseline >25% and to a new QRS > 120 ms
    - New QRS > 120 ms

ECG parameters will be listed, and periods of assessment will be flagged.

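### The SAP's combined transaminase and bilirubin rows ignore baseline, so they can count a participant whose abnormal values predate dosing and never changed

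*Protocol*

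**What the plan says.** Protocol 10.1.2 describes a potential Hy's Law case as "Treatment-emergent elevations in AST or ALT" above 3×ULN, together with bilirubin above 2×ULN or jaundice, where neither cholestasis (ALP is to be below 2×ULN) nor another cause explains the bilirubin. It then lets the Hy's "Law criteria may be changed to increases of transaminases 2-fold above baseline values for subjects with elevated baseline values". For such a case the protocol says: "It must be reported as an SAE to the sponsor promptly".

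SAP 2.6.4, Liver function parameters, says: "The number (%) of participants with worst post-baseline values will be summarized". Two of its categories are combinations: ALT or AST >3×ULN with bilirubin >2×ULN, and the same with the ALP condition added, "ALT or AST > 3xULN & TBL > 2xULN & ALP < 2xULN". The SAP notes that these combinations "are based on the peak values at any post-baseline time for a participant and thus do not need to be concurrent". It states no baseline condition.

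On entry, Protocol 4.4 and 5.2 exclude "Total bilirubin >3 x ULN for age" and low albumin unless prothrombin time is normal. They list no limit for ALT, AST or ALP.

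**The concern.** The two documents share the same three laboratory cut-offs, but the protocol asks for a change on treatment and the SAP asks only for a level after baseline. Entry is open to participants whose level is already there. A combined row can then show a possible drug-induced liver signal in someone whose liver tests did not move. In a trial this small, one entry in that row shapes how the table is read.

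The SAP takes baseline into account in neighbouring summaries. Its ECG categories ask for a new value (for example "New value of > 500 ms") or an increase from baseline, and its notable vital signs in Table 2-1 all require a change from baseline. SAP 2.1.1 already defines baseline as the last assessment up to and including the day of first dosing, so the information needed is available.

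**Working it through.** The documents give no figure for this point, so there is none to reproduce. The check compares the two rules on illustrative values, all in multiples of ULN.

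**Inputs**
- SAP last combined row (SAP 2.6.4): peak ALT or AST >3, peak bilirubin >2, ALP <2, whatever the baseline.
- Protocol rule (10.1.2): the same cut-offs, treatment-emergent. Optionally, if baseline transaminases are raised, a 2-fold rise over baseline.
- Entry (4.4, 5.2): bilirubin up to 3 allowed; no ALT, AST or ALP limit.
- Participants: at least 8 for the primary analysis; 11 enrolled as of 14-Dec-2023 (Protocol Amendment 03).

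**Step 1: can an unchanged participant be counted?** Take ALT 4, bilirubin 2.5 and ALP 1.0 at baseline and at every later visit. Entry is allowed on these values, since 2.5 ≤ 3 and ALT is not restricted. After dosing, 4 > 3, 2.5 > 2 and 1.0 < 2, so both combined rows count the participant. Nothing emerged on treatment, and a doubling would have needed ALT 2 × 4 = 8. The SAP counts this participant; the protocol wording does not make it a case.

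**Step 2: can the fixed transaminase cut-off miss a participant who meets the protocol's option?** Read the phrase as 2 × baseline and take raised to mean above 1×ULN. The option is easier to meet than the fixed cut-off only where 2 × baseline < 3, that is, where baseline < 3/2 = 1.5.

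| Baseline ALT | Peak ALT | 2 × baseline | Meets option (2 ×) | SAP cut-off >3 |
|---|---|---|---|---|
| 1.3 | 2.7 | 2.6 | yes | not met |
| 1.6 | 3.2 | 3.2 | yes | met |
| 4 | 4 | 8 | no | met |

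A miss by this route therefore needs a baseline between 1 and 1.5×ULN. If the phrase instead means reaching 3 × baseline, any raised baseline (>1) requires a peak above 3, and the transaminase cut-off misses no such participant.

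**Step 3: size.** One participant is 1/8 = 12.5 percentage points, or 1/11 = 9.1.

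**The case against.** The strongest reply is that the two texts do different jobs. Protocol 10.1.2 governs what investigators report as an SAE. SAP 2.6.4 sets out laboratory threshold rows that carry no Hy's Law label and, by combining peaks from different visits, are deliberately over-inclusive. Some disagreement with the SAE data is then expected. This stands, and it is why the existing rows should stay as a screen. It does not remove the need to tell the reader which entries were present before dosing.

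The SAP also gives other views of the data. Shift tables compare baseline with the worst on-treatment value for each parameter, and liver values are listed with the assessment period flagged. With about 11 participants, an attentive reader can find a pre-existing abnormality in the listing. That is a real mitigation, but a partial one: the shift tables take one parameter at a time and cannot show whether the combination was new, and the tabulated count remains uncorrected.

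The over-counted participant is hypothetical, needing raised transaminases and bilirubin of 2 to 3×ULN together at entry. The analyses are descriptive and no decision rule uses these rows. The 1/n size would apply to any table in this trial. The ECG comparison is also limited, because the SAP does not define what makes a value new. All of this holds and limits the weight of the point.

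A reader might go further and infer that true Hy's Law cases will be lost. The documents do not support that. Such cases must be reported as SAEs, on-treatment SAEs are summarised and follow-up SAEs are listed (SAP 2.6.1), so at most a case is absent from one descriptive row.

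**Conclusion.** The point holds as a weakness in one descriptive table. The two combined liver rows do not separate abnormality already present before dosing from abnormality that emerged on treatment, and the entry criteria allow the former. Each affected participant moves the row by 12.5 percentage points of 8 or 9.1 of 11. The number affected cannot be stated from the documents.

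The missed-case limb is minor. It requires a baseline transaminase of 1 to 1.5×ULN, the optional criterion actually being applied, and the 2-fold phrase read as 2 × baseline. It is also tempting to say that the SAP contradicts the protocol's Hy's Law definition. That is too strong, because the SAP does not claim that its rows identify such cases. What can be said is that the documents use the same laboratory cut-offs under different conditions, and that the protocol does not say when its optional criterion applies or how the 2-fold rise is to be computed.

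**What to change.** Keep the existing rows in SAP 2.6.4 as the screen. Add a treatment-emergent version of the two combined rows that counts a participant when either:
- the combination was not met at baseline; or
- it was met at baseline and ALT/AST or bilirubin worsened from baseline.

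State in the SAP what counts as worsening, and flag participants whose baseline ALT/AST or bilirubin was already raised.

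The second condition matters. Simply dropping everyone who met the combination at baseline would hide real deterioration. For example, ALT going from 3.5 to 6.5×ULN with bilirubin going from 2.2 to 8×ULN would be dropped, and a 2 × baseline transaminase rule would not recover it, since 2 × 3.5 = 7 > 6.5.

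Separately, reconcile the optional baseline-relative criterion in Protocol 10.1.2 with the SAP rows, so that both documents rest on one stated definition. Which clinical rule that should be is for the sponsor; this review does not choose it.

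The cost of the SAP change is one extra row or flag in one table, from data already collected, with small cells at 8 to 11 participants. If the reconciliation changes the protocol text, it needs an amendment under Protocol 14.1. The SAP addition need not wait for that.

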#### **10.1.3 Adverse Drug Reactions (ADR)**

An ADR is any noxious and unintended response to an IMP related to any dose with at least a reasonably possible causal relationship with the IMP. Briefly, an ADR is an AE which is suspected to be possibly related to IMP by either the investigator or the study sponsor.

#### **10.1.4 Suspected Unexpected Serious Adverse Reactions (SUSARs)**

An ADR will be assessed to be “unexpected” if the nature, severity or frequency of the event is not consistent with the applicable product information available for the IMP. An ADR will be assessed to be “expected” if it is listed in the Investigator’s Brochure.

A SUSAR is an adverse event regarded as serious with at least possible causal relationship to the drug, the nature, severity or frequency of which is not consistent with the applicable information available in the reference documents available for the IMP.

#### **10.1.5 Adverse Events of Special Interest**

Adverse events of special interest (AESI) are defined as events (serious or non-serious) which are ones of scientific and medical concern specific to the Sponsor’s product or program, for which ongoing monitoring and rapid communication by the Investigator to the Sponsor may be appropriate. Such events may require further investigation in order to characterize and understand them.

These potential risks deserve special attention even if they do not fulfill any of the seriousness criteria. These non-serious adverse events of special interest (AESI) should be reported to the Sponsor using reporting procedures for SAEs. During screening, only AESI meeting seriousness criteria should be reported to the Sponsor. During the treatment period, all AESI need to be reported to the Sponsor irrespective of causality. During the follow-up period, AESI need to be reported only if considered related to the study treatment except for all secondary malignancies which need to be reported as AESI irrespective of causality. The AESI represent main risks of Lutathera and amino acid treatment reported in adults, as well as potential risks in pediatric population ([Table 10-1](#)).

**Table 10-1 Adverse events of special interest**

| AESI categories                          |
|--|
| Secondary malignancies                   |
| Hematotoxicities                         |
| Nephrotoxicities                         |
| Endocrine disorders                      |
| Bone development disorders               |
| Cardiovascular and electrolyte disorders |

**Secondary malignancies:** any secondary malignancies, including MDS and acute myeloid leukemia, should be reported in every case irrespective of causality, as AESI/SAE, until the end of long-term follow up period.

**Hematotoxicity:** The main critical organ of Lutathera treatment is the bone marrow. Significant hematotoxicity, defined as Grade 2 or higher thrombocytopenia, or Grade 3 or 4 of any other hematotoxicity (anaemia, leuko-/lympho-/neutropenia) are considered dose-modifying toxicities in the study and must be reported as AESI when not strictly fulfilling the criteria of serious adverse events. Haematological toxicities regardless of severity must be reported as AESI if accompanied by clinical consequences, i.e., infections in the presence of leuko-/neutro-/lymphopenia, hemorrhages / purpuric lesions under thrombocytopenia that is not explained by another coagulation disorder, dyspnea / fatigue in the presence of anaemia not otherwise explained by the underlying carcinoid syndrome or other co-morbidity.

**Nephrotoxicity:** Since Lutathera is cleared through the kidneys and reabsorbed by the kidneys, the kidneys have always been considered the “critical organs”. An infusion of amino acid is used for kidneys protection by inhibition of tubular reabsorption of Lutathera. Pursuant to these risk minimization efforts and in addition to the criteria of dose-modifying toxicities and criteria of inclusion (at baseline and before subsequent treatments) pertinent to renal function measurements, renal and urinary tract toxicities are considered AESI. Investigators must report as AESI renal toxicities including renal failure (ranging from significantly reduced measured or estimated creatinine clearance to clinically overt renal failure other than that of obvious non-IMP-induced origin), suspected radiation nephropathy of any type, such as radiation-induced thrombotic microangiopathy (manifested with, e.g., proteinuria, hypertension, edema, anaemia, decrease serum haptoglobin), or general symptoms and signs of acute radiation toxicity (e.g., increased frequency and urgency of urination, nocturia, dysuria, bladder spasm, bladder obstruction, genitourinary ulceration or necrosis).

**Endocrine (hypothalamic-pituitary and growth) disorders:** Since the potential effect of the Lutathera treatment on the pituitary-gonadal and pituitary-thyroid axes is not well described in the adolescent population, the endocrine effects will be closely monitored via specific biomarkers. Any suspected endocrine toxicity should be considered AESI regardless of severity.

**Effects on bone development:** Radiation exposure has a potential effect on the overall quantity and quality of bone by interfering with the trabecular architecture through increased osteoclast activity and decreased osteoblast activity. Biomarkers of bone metabolism help to detect the metabolic imbalance and identify bone toxicities. Any suspected bone toxicity should be considered AESI regardless of severity.

### **Cardiovascular and electrolyte disorders:**

All clinically significant changes in blood pressure, heart rate, electrocardiogram and electrolyte parameters must be reported as AESI if they occur within reasonable propinquity of Lutathera or sterile amino acid solution administration in the judgment of the Investigator. Likewise, clinically manifest consequences of hypo-/hypertension, arrhythmias, cardiac conduction disturbances, electrolyte disorders and other cardiac pathologies evidenced by objective findings / changes on electrocardiogram or echocardiography should also be considered for AESI reporting.

#### **10.1.6 SAE and AESI reporting**

##### **SAE reporting:**

To ensure subject safety, after the patient signed the informed consent and before the patient received a study drug, only SAE potentially related to any study procedure must be reported. After the first dose of study drug(s), all SAEs regardless of suspected causality and until 30 days after the EoT visit must be reported to the Sponsor within 24 hours of learning of its occurrence. Afterwards, any SAEs experienced during the Follow-up period should only be reported to the Sponsor if the investigator suspects a causal relationship to study treatment.

Detailed instructions regarding the submission process and requirements are to be found in the investigator folder provided to each site.

All follow-up information for the SAE including information on complications, progression of the initial SAE and recurrent episodes must be reported as follow-up to the original episode within 24 hours of the investigator receiving the follow-up information. An SAE occurring at a different time interval or otherwise considered completely unrelated to a previously reported one must be reported separately as a new event.

Information about all SAEs is collected and recorded on the SAE Form; all applicable sections of the form must be completed in order to provide a clinically thorough report. The investigator must assess and record the relationship of each SAE to each specific study treatment (if there is more than one study treatment), complete the SAE Report Form in English, and submit the completed form within 24 hours to the Sponsor.

Follow-up information is submitted in the same way as the original SAE Report. Each reoccurrence, complication, or progression of the original event should be reported as a follow-up to that event regardless of when it occurs. The follow-up information should describe whether the event has resolved or continues, if and how it was treated, and whether the patient continued or withdrew from study participation.

If the SAE is not previously documented in the Investigator's Brochure or Package Insert (new occurrence) and is thought to be related to the study treatment, the Sponsor may urgently require further information from the investigator for health authority reporting. The Sponsor may need to issue an Investigator Notification (IN) to inform all investigators involved in any study with the same study treatment that this SAE has been reported.

Suspected Unexpected Serious Adverse Reactions (SUSARs) will be collected and reported to the competent authorities and relevant ethics committees in accordance with EU Guidance 2011/C 172/01 and EU Clinical Trial Regulation 536/2014 (once transitioned under EU CTR) or as per national regulatory requirements in participating countries.

All SAEs related to any authorized auxiliary medicinal product (whether authorized or not) used in this study must be reported to Advanced Accelerator Applications within 24 hours of the site becoming aware of it. In assessing causality, the investigators will use the points above. If a suspicion that medical occurrence could be related to study treatment (and/or interaction with study treatment) cannot be ruled out, the reporting rules for study treatment apply. AxMP safety reporting requirements will only apply once the trial has been transitioned under EU Clinical Trial Regulation 536/2014.

### **AESI reporting:**

During screening, only AESI meeting seriousness criteria should be reported. During the treatment period, all AESI need to be reported to the Sponsor irrespective of causality within 24 hours. During the follow-up period, AESI need to be reported only if considered related to the study treatment except for all secondary malignancies which need to be reported as AESI irrespective of causality.

For all reportable AESI irrespective of their seriousness, SAE form will be completed and submitted to the sponsor within 24 hours.

